9.2.2. Sample Size Sensitivity

The estimated 9.3% annual MACE rate is based on a blinded summary of ASCEND-ND data as of April 20, 2020. Table 11 illustrates the impact on power if the true underlying treatment effect is not a hazard ratio of 0.97.

Table 11 Sensitivity Based on a Different True Underlying Treatment Effect

Underlying hazard ratio for MACE rate	Power for non-inferiority
0.90	99%
0.95	94%
0.97 (base case)	90%
1.00	82%
1.03	70%
1.05	61%

Impact of Sample Size for Hgb Efficacy Analysis

Subjects will be treated to achieve and maintain a Hgb between 10-11 g/dL. The expected difference in mean Hgb change from baseline between arms and the EP is 0 g/dL and the anticipated standard deviation (SD) is 1.5 g/dL, based on historical rhEPO trials and daprodustat clinical trial experience to date.

For 90% power to test the co-primary non-inferiority Hgb hypothesis, with a two-sided 95% CI, pre-specified margin of -0.75 g/dL and a two-sample T-test, a total of 86 evaluable subjects per treatment group are required. The planned study size far exceeds this requirement and the analysis will have more than 99% power for non-inferiority and a high level of precision to estimate the treatment effect (two-sided 95% CI half width is expected to be approximately 0.105 g/dL, assuming a 30% non-evaluable rate for efficacy). The largest (most negative) difference between arms that would meet the statistical criterion for non-inferiority would be -0.645 g/dL. If the two-sided 95% CI is completely negative (i.e. lies fully within the range -0.75 to <0 g/dL) non-inferiority would still be concluded.

9.2.3. Sample Size Re-estimation or Adjustment

GSK and the Executive Steering Committee will review blinded data periodically during the course of the study and should emerging data suggest that the overall event rate and/or the enrollment rate (main study or sub-studies) diverges significantly from protocol assumptions either the sample size required to achieve the event target and/or the requirement for a minimum of one year follow-up may be adjusted.

The current COVID-19 pandemic has significantly impacted subject enrolment such that it is considered likely that enrolment will be closed prior to reaching the target of 4,500 subjects.

9.3. Data Analysis Considerations

9.3.1. Analysis Populations

The primary population for all analyses of MACE and other time to event outcomes will be the All Randomized (ITT) Population. Subjects will be analyzed according to the treatment to which they were randomized.

The primary population for the Hgb efficacy analyses will also be the ITT Population. A supportive analysis of the primary efficacy endpoint will be performed in a Per-Protocol (PP) Population defined as all ITT subjects who are not major protocol violators. Details will be defined in the RAP and subjects analyzed according to the treatment received.

The primary population for safety will be based on all randomized subjects who receive at least one dose of randomized treatment. Subjects will be analyzed according to the treatment received.

Additional populations may be defined in the RAP, including sub-study populations.

9.4. Key Elements of Analysis Plan

9.4.1. Primary Analyses

9.4.1.1. Primary CV Safety Analysis (co-primary)

MACE: The co-primary cardiovascular safety analysis is to assess the comparative treatment effect for time to first occurrence of adjudicated MACE in all randomized subjects. Time to the first occurrence of a primary endpoint event will be computed as (event date – randomization date) +1. Subjects who do not have the event during the trial period will be censored in the analysis, with details provided in the RAP. The statistical model is a Cox-Proportional-Hazards-Regression model, adjusting for treatment and the prognostic randomization stratification factors (region and current ESA use), to estimate the hazard ratio, two-sided 95% CI and one-sided p-value for the statistical non-inferiority test. Non-inferiority will be established if the upper limit of the two-sided 95% CI is less than the margin of 1.25. Cumulative time from randomization to first event or end of trial will be evaluated using Kaplan-Meier methodology and displayed graphically. Treatment comparisons from the Cox regression model will be presented as hazard ratios and two-sided 95% CIs and displayed on forest plots. The validity of the proportional hazards assumption will be assessed. All adjudicated events will be used for the primary analysis and concordance between investigator reported and adjudicated events will be summarized.

Sensitivity and Supportive Analyses: A sensitivity analysis will be performed to address potential effects of drop outs and to evaluate the robustness of the co-primary MACE analysis. A sensitivity “tipping point” analysis utilizing multiple imputation for randomized subjects who have withdrawn from the study will be performed as well as a supportive “on-drug” analysis to evaluate the comparative treatment effect during the time that subjects remain on randomized treatment (plus a window of 28 days). Full details will be provided in the RAP.

In addition, analyses of MACE as described above will be performed for each component of MACE (all-cause mortality, MI and stroke) to understand individual contributions to the overall MACE result and to assess component directional consistency. These analyses will not be multiplicity adjusted. Further subgroup and covariate adjusted analyses of specific clinical interest are described in Section 9.4.4

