9.2. Sample Size Considerations

9.2.1. Sample Size Assumptions

The size of this event driven trial is based on the co-primary CV safety objective and is determined by a fixed event target of 664 adjudicated first MACE. This provides approximately 90% power to establish non-inferiority assuming a true underlying 3% lower relative risk of MACE in favor of daprodustat compared to darbepoetin (i.e., hazard ratio=0.97) and 82% power for non-inferiority under the assumption that the true underlying risk of MACE is the same in both arms (i.e., hazard ratio=1). Other assumptions behind the sample size calculation include:

- Projected annual adjudicated first MACE rate of 9.3%. All-cause death is expected to be the most prevalent component, followed by non-fatal MI and then non-fatal stroke (projected break down of 50%, 30% and 20% respectively).
- Variance under the alternative hypothesis (i.e. hazard ratio=0.97)
- 1% annual lost to follow-up without vital status
- A two-sided 95% CI is used for analysis

The target of 664 adjudicated first MACE will permit a two-sided 95% CI of (0.859, 1.164) to describe the results for an observed hazard ratio of 1. The largest hazard ratio point estimate (two-sided 95% CI) that would meet the statistical criterion for non-inferiority is 1.074 (0.922, 1.250) and for superiority, the minimum observable effect would be a 14.1% relative risk reduction in favor of daprodustat, corresponding to a hazard ratio of 0.859.

Conditional on both co-primary endpoints achieving non-inferiority at the one-sided 2.5% level, statistical testing will progress to evaluate MACE and the principal secondary endpoints for superiority. These tests will be multiplicity adjusted, details are provided in Section 9.4.3.

Based on expected enrolment and an annual MACE rate of 9.3%, it is anticipated that the the 664 adjudicated first MACE target will be reached approximately 4.2 years from when the first subject is randomized. It is anticipated that more than 80% of randomized subjects will have the opportunity for a minimum of 1 year exposure to treatment and thus the opportunity to complete the EP (Weeks 28 to 52). Exposure to daprodustat is expected to be in the region of 4000 patient years with median patient follow-up expected to exceed 2 years.

Note: The country-specific requirements for France ONLY for the sample size consideration are provided in [Appendix 15](#) (see Section 12.15.1, Item 2 for details).

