9.4.2. Secondary Analyses

9.4.2.1. Principal Secondary Analyses

Conditional on the co-primary endpoints achieving non-inferiority at the one-sided 2.5% level, statistical testing will progress to superiority for MACE and the principal secondary endpoints. The hypotheses to be tested for these endpoints are as follows:

- **Null:** daprodustat is not superior to darbepoetin alfa (i.e. the hazard ratio is greater than or equal to 1.0 for time-to-event endpoints, or the mean difference is greater than or equal to 0 for continuous endpoints)

- **Alternative:** daprodustat is superior to darbepoetin alfa (i.e. the hazard ratio is less than 1.0 for time-to-event endpoints, or the mean difference is less than 0 for continuous endpoints)

These tests will be multiplicity adjusted based on a family-wise Type I error rate set at the one-sided 2.5% level, see Section 9.4.3 for further details.

The principal secondary endpoints are listed below. The statistical modeling approach described for MACE in Section 9.4.1.1 will be repeated for these adjudicated composite events:

- MACE or a thromboembolic event (vascular access thrombosis, symptomatic deep vein thrombosis or symptomatic pulmonary embolism)
- MACE or hospitalization for HF

The progression of CKD endpoint is as follows:

- Progression of CKD [40% decline in eGFR from baseline (confirmed 4-13 weeks later) OR ESRD]

ESRD definition: a) initiating chronic dialysis for ≥ 90 days or b) not initiating chronic dialysis when dialysis is indicated (adjudicated) or c) receipt of a kidney transplant. *adjudicate only if the duration of dialysis is < 90 days.*

This endpoint will be restricted to the subset of subjects with $eGFR \geq 15$ ml/min/1.73m² at baseline. Since all-cause mortality is not included as a component of the composite endpoint, Fine and Gray's subdistribution hazards analysis model will be used to account for this competing risk and the cumulative incidence function accounting for this competing risk of death will be provided. Further details will be provided in the RAP. *For sensitivity, all-cause mortality will be included in the composite endpoint and traditional Kaplan-Meier methodology applied for analysis.*

Additional secondary endpoints are listed in Appendix 2. All analyses of secondary endpoints are of exploratory nature, summary statistics and nominal one-sided p-values will be used for any treatment comparisons.

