12.2. Appendix 2: Secondary and Exploratory Objectives/ Endpoints

Objectives	Endpoints
Secondary Objectives	Secondary (tested for superiority¹, no multiplicity adjustment)

 To compare daprodustat and darbepoetin alfa on additional CV safety endpoints 	
 All-cause mortality, CV mortality, fatal or non-fatal MI, fatal or non-fatal stroke² MACE or hospitalization for HF² (recurrent events analysis) CV mortality or non-fatal MI² All-cause hospitalization All cause hospital re-admission within 30 days MACE or hospitalization for HF or thromboembolic events² Hospitalization for HF² Thromboembolic events² Individual components of CKD progression²

 To compare daprodustat to darbepoetin alfa on Hgb variability 	
 Hgb change from baseline to Week 52¹ N (%) responders, defined as mean Hgb within the Hgb analysis range 10-11.5 g/dL during EP % time Hgb in analysis range (10-11.5 g/dL) during the EP (Week 28 to 52) and during the maintenance period (MP; Week 28 to end of trial) [non-inferiority analysis that will use a margin of 15% less time in range]¹

 To compare daprodustat to darbepoetin alfa on BP 	
 Change from baseline in SBP, DBP and MAP at Week 52 and at end of treatment Number of BP exacerbation events per 100 patient years N (%) with at least one BP exacerbation event during study

 To compare daprodustat to darbepoetin alfa on the time to rescue (defined as permanently stopping randomized treatment and due to meeting rescue criteria) 	
 Time to stopping randomized treatment due to meeting rescue criteria

 To compare daprodustat to darbepoetin alfa on HRQoL and Utility score 	
 Mean change in SF-36 HRQOL scores (Physical Component Score [PCS], Mental Component Score [MCS] and 8 health domains) between baseline and Weeks 8, 12, 28, 52, of particular interest are the changes from baseline in the vitality and physical functioning domains at Weeks 28 and 52 Change from baseline in Health Utility (EQ-5D-5L) score at Week 52 Change from baseline in EQ VAS at Week 52

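### Section 9.4.1.1 carries Kaplan-Meier over from MACE to MI and stroke, where death from other causes competes, so their cumulative incidence is modestly overstated

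*Protocol*

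**What the plan says.** Protocol Section 9.4.1.1 sets the MACE analysis: a Cox model for the treatment comparison, plus a display for which "Cumulative time from randomization to first event or end of trial will be evaluated using Kaplan-Meier methodology and displayed graphically". On censoring it says: "Subjects who do not have the event during the trial period will be censored in the analysis, with details provided in the RAP". It then states that "analyses of MACE as described above will be performed for each component of MACE (all-cause mortality, MI and stroke". The stated purposes are to show what each component contributes to the MACE result and whether the components point the same way. These analyses carry no multiplicity adjustment.

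Appendix 2 lists the component endpoints as "All-cause mortality, CV mortality, fatal or non-fatal MI, fatal or non-fatal stroke". Fatal MI and fatal stroke therefore count as events there, while deaths from any other cause do not.

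For progression of CKD, Section 9.4.2.1 reasons: "Since all-cause mortality is not included as a component of the composite endpoint". It therefore uses the Fine and Gray model and promises that "the cumulative incidence function accounting for this competing risk of death will be provided". Kaplan-Meier is kept for the sensitivity version that adds death to the composite.

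**The concern.** Kaplan-Meier treats a censored subject as still able to have the event later. That is reasonable for a subject who has reached the end of the study, but not for one who has died. If deaths from other causes are censored in the MI analysis, 1 minus Kaplan-Meier estimates the incidence of MI in a hypothetical population in which nobody dies of anything else. This always lies above the proportion of randomized subjects who have an MI, and the gap widens with follow-up.

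The protocol expects deaths to make up half of first MACE, so the competing event is common. One purpose of the component displays is to show how much MI and stroke add to MACE, which is a question about incidence as it occurs. Section 9.4.2.1 accepts this argument for CKD progression in the same trial, and Section 9.4.1.1 makes no matching provision for MI and stroke.

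**Working it through.** **The plan's own figures.** The protocol gives no cumulative incidence for MI or stroke, so there is nothing to reproduce on this exact point. The design figures do reproduce. For margin 1.25, true hazard ratio 0.97, one-sided 2.5% and 90% power, 4 × (1.960 + 1.282)² / [ln(1.25/0.97)]² gives 654 events, against the stated 664. With 664 events the power is 90.5% at 0.97 and 82.0% at 1.00, as stated.

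**Inputs.**
- "Projected annual adjudicated first MACE rate of 9.3" per cent (Section 9.2.1), taken as a constant hazard of 0.093 per year.
- Death, non-fatal MI and non-fatal stroke in a "projected break down of 50%, 30% and 20% respectively" (Section 9.2.1). Hazards: death d = 0.0465, MI = 0.0279, stroke = 0.0186 per year.
- Trial length about 4.2 years, median follow-up expected to exceed 2 years, 1% annual loss to follow-up (Section 9.2.1), 2250 subjects per arm (Section 4.2).

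**Formulas.** With c the MI or stroke hazard:
- 1 minus Kaplan-Meier, deaths censored: 1 − exp(−ct)
- True cumulative incidence: c/(c+d) × [1 − exp(−(c+d)t)]

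For MI at 3 years the first is 1 − exp(−0.0837) = 8.03%. The second is 0.375 × [1 − exp(−0.2232)] = 7.50%.

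| Time | MI: 1−KM | MI: true | Excess | Stroke: 1−KM | Stroke: true | Excess | Relative excess |
|---|---|---|---|---|---|---|---|
| 2 years | 5.43% | 5.18% | 0.24 | 3.65% | 3.49% | 0.16 | 4.7% |
| 3 years | 8.03% | 7.50% | 0.53 | 5.43% | 5.07% | 0.36 | 7% |
| 4.2 years | 11.06% | 10.06% | 0.99 | 7.51% | 6.84% | 0.68 | 9.9% |

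Excesses are in percentage points, taken before rounding. As a check, the relative excess is roughly dt/2, which gives 4.7%, 7.0% and 9.8%. Simulating Kaplan-Meier against Aalen-Johansen for MI in 400,000 subjects gave 4.7%, 7.0% and 9.5% at 2, 3 and 4 years. Reading 9.3% as an annual probability, so a hazard of −ln(1 − 0.093) = 0.0976, changes little: MI 4.9%, 7.4% and 10.4% at 2, 3 and 4.2 years.

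**Against sampling error.** The large-sample Greenwood standard error of Kaplan-Meier is exp(−ct) × √{∫₀ᵗ c / [n exp(−(c+d)u) G(u)] du}. Here n = 2250 and G(u) = min(1, (4.2 − u)/a) × exp(−0.01u), with uniform entry over a = 3.2 to 3.8 years (assumed). For MI:
- 3 years: standard error 0.71 to 0.76 points, so the excess of 0.53 is about 0.7 of it.
- 4 years: standard error 1.12 to 1.21 points, excess 0.91, about 0.75 to 0.8 of it.

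For stroke the ratio is about 0.6 at both times. Only 0.2/a, about 5 to 6% of subjects, could have 4 years of follow-up.

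**Range for the competing hazard.** The base case counts only deaths that are a first MACE. Deaths after another type of first event, such as a stroke in the MI analysis, would raise it. Counting fatal MI and fatal stroke as events, as in Appendix 2, would lower it. If it were 1.5 to 2 times higher (assumed), the relative excess would be about 7 to 9.5% at 2 years and 15 to 20% at 4.2 years.

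**The case against.** **The details are left to the RAP.** Censoring at death is not written out for the components, and the plan defers censoring details. That much stands. But the estimator is not deferred: Kaplan-Meier is named, the whole analysis is carried over to each component, and nothing exempts MI or stroke. A reader following Section 9.4.1.1 as written would censor these deaths.

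**The effect is small and no inference depends on it.** This also stands. At the expected median follow-up the excess is about a quarter of a point for MI. With similar mortality, both arms shift almost equally. The components are supportive.

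**CKD progression deserves fuller treatment as a multiplicity-controlled endpoint.** That is a fair reason for a Fine and Gray model there and not here. It does not explain why the cumulative incidence display, which Section 9.4.2.1 also justifies by death lying outside the endpoint, should differ for MI and stroke.

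**Stronger readings a reader might infer.** The documents do not support these three:
- *A mortality difference between arms distorts the Kaplan-Meier gap.* The formula 1 − exp(−ct) contains no death hazard, so with equal MI hazards that gap is zero under the model used here. It is the cumulative incidence that moves. With equal MI hazards and 25% higher mortality in one arm, MI incidence at 4.2 years is 9.83% against 10.06%. So a cumulative incidence gap cannot by itself show directional consistency.
- *The component curves should add up to the MACE curve.* The components overlap, since a subject can have an MI and later die. At 3 years the sum is 26.5% with Kaplan-Meier throughout and 25.6% after the correction, against 24.3% for MACE.
- *The same fault affects heart failure hospitalization, thromboembolic events and CV mortality.* No section prescribes Kaplan-Meier for these. Section 9.4.2.1 promises only summary statistics and nominal p-values for the additional secondary endpoints.

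**Conclusion.** The point holds, as a modest one. Section 9.4.1.1 states a method that overstates the cumulative incidence of MI and stroke in one direction, by an amount that grows with follow-up and does not shrink with sample size. It also conflicts with the reasoning of Section 9.4.2.1. The sizes in the table rest on constant hazards at the protocol's projected rate and split, with a competing hazard equal to the projected rate of death as first MACE.

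Nothing confirmatory is touched. The Cox model with deaths censored gives a valid cause-specific hazard ratio for MI and stroke, so the directional check based on hazard ratios stands. MACE and all-cause mortality include every death as an event, and Kaplan-Meier is right for them.

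**What to change.** Add one sentence to Section 9.4.1.1. For MI and stroke, cumulative incidence is displayed by the Aalen-Johansen estimator with death from other causes as the competing event, alongside the Cox cause-specific hazard ratio. State that the hazard ratio remains the basis for judging directional consistency, because a cumulative incidence gap can also reflect a mortality difference. Keep Kaplan-Meier for MACE and all-cause mortality.

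The cost is negligible. The protocol already commits to a cumulative incidence function for CKD progression, no extra data are needed, and no hypothesis test or sample size changes. The reported MI and stroke incidences become slightly lower.

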9.4.1.2. Primary Efficacy Analysis (co-primary)

Mean change in Hgb between baseline and the EP (Weeks 28 to 52): The primary efficacy estimand is the effect of daprodustat relative to darbepoetin alfa on the change in Hgb from baseline to the average of all values in the EP, regardless of adherence to treatment including interruptions and discontinuation, the use of non-randomized ESA medication for any reason including rescue therapy, or the use of blood transfusions, in subjects not on dialysis with anemia secondary to CKD and assuming subjects do not die before the end of the EP. The analysis will use an analysis of covariance (ANCOVA) model. For each subject, baseline Hgb will be the value obtained on Day 1, prior to taking randomized treatment, and Hgb during EP will be determined by calculating the mean of all available and imputed Hgb values between Weeks 28 to 52 inclusive regardless of adherence to randomized treatment. The ANCOVA model will include prognostic randomization stratification factors (region and current ESA use), baseline hemoglobin and treatment. It will provide a point estimate and two-sided 95% CI for the treatment effect together with the one-sided non-inferiority test p-value. Non-inferiority will be established if the lower limit of the two-sided 95% CI is greater than the margin of -0.75 g/dL. Imputation will be used for missing Hgb data; further details will be provided in the RAP.

Sensitivity and Supportive Analyses: Sensitivity analyses for the primary estimand will include a multiple imputation-based “tipping point” analysis where assumptions are adjusted until non-inferiority is lost by imputing data for subjects who did not fully complete the EP. A supportive analysis will evaluate efficacy in those subjects who adhere to randomized treatment, defined as subjects with at least one on-treatment Hgb during the EP (this approach corresponds to evaluating an efficacy estimand). A supportive “tipping point” analysis as that described above for the primary analysis will be performed for this “on-drug” analysis. In addition, a per-protocol supportive analysis will estimate the treatment effect in subjects who strongly adhere to the protocol, and supportive analyses to explore a shorter EP (Weeks 28 to 36) will be performed for the co-primary effectiveness estimand and “on-drug” efficacy estimand. Full details of all sensitivity and supportive analyses will be provided in the RAP.

9.4.2. Secondary Analyses

9.4.2.1. Principal Secondary Analyses

Conditional on the co-primary endpoints achieving non-inferiority at the one-sided 2.5% level, statistical testing will progress to superiority for MACE and the principal secondary endpoints. The hypotheses to be tested for these endpoints are as follows:

- **Null:** daprodustat is not superior to darbepoetin alfa (i.e. the hazard ratio is greater than or equal to 1.0 for time-to-event endpoints, or the mean difference is greater than or equal to 0 for continuous endpoints)

- **Alternative:** daprodustat is superior to darbepoetin alfa (i.e. the hazard ratio is less than 1.0 for time-to-event endpoints, or the mean difference is less than 0 for continuous endpoints)

These tests will be multiplicity adjusted based on a family-wise Type I error rate set at the one-sided 2.5% level, see Section 9.4.3 for further details.

The principal secondary endpoints are listed below. The statistical modeling approach described for MACE in Section 9.4.1.1 will be repeated for these adjudicated composite events:

- MACE or a thromboembolic event (vascular access thrombosis, symptomatic deep vein thrombosis or symptomatic pulmonary embolism)
- MACE or hospitalization for HF

The progression of CKD endpoint is as follows:

- Progression of CKD [40% decline in eGFR from baseline (confirmed 4-13 weeks later) OR ESRD]

ESRD definition: a) initiating chronic dialysis for ≥ 90 days or b) not initiating chronic dialysis when dialysis is indicated (adjudicated) or c) receipt of a kidney transplant. *adjudicate only if the duration of dialysis is < 90 days.*

This endpoint will be restricted to the subset of subjects with $eGFR \geq 15$ ml/min/1.73m² at baseline. Since all-cause mortality is not included as a component of the composite endpoint, Fine and Gray's subdistribution hazards analysis model will be used to account for this competing risk and the cumulative incidence function accounting for this competing risk of death will be provided. Further details will be provided in the RAP. *For sensitivity, all-cause mortality will be included in the composite endpoint and traditional Kaplan-Meier methodology applied for analysis.*

Additional secondary endpoints are listed in Appendix 2. All analyses of secondary endpoints are of exploratory nature, summary statistics and nominal one-sided p-values will be used for any treatment comparisons.

